The randomization will be in block, in which there will be permutation in the order and size of the blocks. The randomization will be generated through the website www.randomization.com by a researcher who will not be directly linked to the research. Patient allocation will be done through sealed, opaque and standardized envelopes. After the patient signs the informed consent form, the envelope will be opened and the envelope will be allocated to the treatment, in a coded form. The envelope will be identified with a random number that will be assigned to each patient.

Inclusion and exclusion criteria

Patients older than 60 years, with initial HDRS greater than 17, who have MDD. The exclusion criteria will be: other mental disorders (alcohol or drug addiction, psychotic disorders, dementia, bipolar disorder); presence of serious neurological or clinical diseases; presence of severe suicidal ideation and CIRS (Cumulative Illness Rating Scale) score > 7, characterizing a set of clinical morbidities that could impair adherence to the research protocol. In addition, specific contraindications to the use of rTMS will also be excluded, such as: metal implants, epilepsy or electronics in the cephalic segment. Patients who are receiving antidepressants will have a wash-out of five half-lives of the medications prior to entry into the study. Patients receiving benzodiazepines will be included since receiving a maximum dose of 10mg of diazepam or equivalent. Other psychoactive drugs will be accepted as long as the doses of the medications have been stable for at least 6 weeks.

Blinding

The study will be double-blind, evaluators and patients will not be aware of the randomized treatment until the end of the study. The blinding will be done with a sham coil, which consists of a coil that reproduces the sound that the true coil does, but without generating the magnetic field. A person only intended to apply the rTMS session will do the procedure and will not be involved with the evaluations or with the evaluators, this person will be also blinded. A blinding scale will be applied to evaluators, applicators, and volunteers to evaluate if the blinding was effective.

Interventions

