The coil will be positioned in the prefrontal dorsolateral cortex, with intermittent TBS (TBSi) mode on the left and continuous TBS (TBSc) on the right (F3 and F4 positions determined by the 10–20 Electroencephalographic International System). 1800 pulses will be used on each side, totaling 11 minutes 39 seconds of total duration. TBS will have the following parameters: in cTBS bursts of three pulses at 50 Hz (20-ms interval between stimuli) will be applied continuously for 120 s total in the right DLPFC and iTBS bursts of three pulses at 50 Hz (20-ms interval between stimuli) will be applied for 2-s duration repeated every 10 s for a total time of 570 s also totaling 1800 pulses in the left DLPFC, both with 120% of motor threshold. We will use a magnetic stimulator device (MagVenture©) in study mode for double-blind trials. The coil has a side that is active and the other is sham. The applicant of TMS will be blinded too (after placing the coil over the patient's head and entering his number, the device tells if the position is correct or if you have to turn it, but the applicant does not know externally what is the sham side of the coil). The sham produces the same sound as the real one. We also put on the head electrodes that give stimulus to mimic the real magnetic coil (both groups receive this). There will be

20 consecutive sessions, one per day, except on weekends and holidays, totaling around 4 weeks. A day of stimulation with the same technique will be done in the 6th week, 8th week and 12th week.

Clinical variables

We will use the MINI questionnaire for the diagnosis of psychiatric disorders, applied by an experienced psychiatrist. It is translated and validated into the Portuguese language³⁹. The demographic and clinical profile of the patients will be evaluated by: gender, age, schooling, socioeconomic status, clinical comorbidities, use and dose of antidepressants and other psychoactive drugs.

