The main outcome will be measured using the HDRS scale. The primary evaluation will be done at the end of 6 weeks from the start of the first day of TBS. As secondary outcomes we will use the GDS (Geriatric Depression Scale), Cumulative Illness Rating Scale (CIRS), the global clinical impression scale (CGI), Positive and Negative Affect Scale (PANAS), Montgomery-Asberg Depression Rating Scale (MADRS), and Edinburgh Handedness Inventory (EHI). All scales have already been translated and validated into Portuguese⁴⁰. Outcomes will be measured on 7 occasions: baseline after 1, 2, 4, 6, 8 and 12 weeks of study entry. The presence of adverse effects and the Young mania (YMRS) questionnaire will also be evaluated to detect manic and / or hypomanic cycling.

Cognitive Assessments

The cognitive battery will be applied by experienced neuropsychologists. For cognitive assessments they will be exploratory, secondary outcomes will be measured on the baseline, on the 20th day of the session and the addenbrooke cognitive examination will also be reapplied on the 12th week. We will use the Addenbrooke's Cognitive Examination - Revised Version (ACE-R), Ravlt - Word List, Rey's complex figure, Stroop Test (violet version); Wais III - Subtest Codes; Trail Making A and B and WASI - Vocabulary and Matrix Reasoning subtest.

Biomarkers

BDNF (brain-derived neurotrophic factor) is implicated in the pathophysiology of depression. Recent meta-analyses have shown that depressed patients have lower serum levels of BDNF than normal subjects^{41,42}. The samples will be collected in dry tubes, centrifuged within two hours after collection, then separate the serum and refrigerate it in eppendorfs at -70oC in liquid nitrogen. The samples will therefore be stored in a cryogenic bank. They will be collected at the beginning of the study and in the 6th week.

Cerebrospinal fluid (CSF) samples will be collected by means of a lumbar puncture during the evaluation procedures before the intervention begins. They will be used for the investigation of beta-amyloid peptide (Aβ1-42) and Tau protein (total and phosphorylated). These determinations will allow

the analysis of the interaction between the presence of Alzheimer's disease pathology and the therapeutic response to the TBS intervention.

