Actigraphy consists of a wrist device equipped with an accelerometer, a microprocessor and an internal memory, which are capable of detecting and storing the movement record. It is used in the evaluation of sleep disorders such as diseases of circadian rhythm, insomnia and excessive daytime sleepiness. We will use the actigraphy on the left wrist of the volunteers 1 week before the beginning of the research and for another 4 weeks after the study. The objective is to assess sleep changes associated with the clinical response to magnetic stimulation.

Pupil Examination (PLR) the participant will do a test lasting about 20 minutes in which a camera phone will record the size of your pupil during this period while you will hear some sounds. The exam is painless and without side effects.

Sample size calculation:

Based on the clinical trial of Li⁴³, which demonstrated an efficacy favoring bilateral TBS in depression of 52.5% for the active group and 17.4% for the sham group, for a two-tailed p 0.05 and a power of 90%, the total sample size is 86 subjects. Considering a rate of friction of approximately 25%, we estimated the final sample size in 108 patients.

Statistical analysis

Statistical analysis will be performed with the Stata 16 SE program for Mac OS X. All analyzes will be made on the intention to treat principle (ie the data of all participants will be included in the analysis) in which lost data will be allocated according to the last observation carried forward principle and/or mixed data. Analyzes will be considered significant at p <0.05. We will use parametric tests to analyze the main outcomes, which are allowed by the sample size. Number of previous admissions, presence of clinical comorbidities, refractoriness (measured by the Massachusetts General Hospital scale - MGH-S)⁴⁴ will be analyzed as ordinal data. For the main outcome we will use a repeated measures analysis, having HDRS scores as Dependent variable and TBS as independent variable at week 8. Secondary analyses of the other scales and biomarkers will be performed in the same way, replacing HDRS as a dependent variable.

Study Flow Chart

We show below the flowchart for each patient throughout the study. It is worth remembering that TBS will be applied 23 times: 20 consecutive sessions (week 0 through week 4), 6th week, 8th week and 12th week. Still, patients who receive *sham* stimulation and who are still depressed may receive active stimulation at the end of the study.

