Table 1. Study schedule

	Triage	Baseline	Week						
			1	2	3	4	6	8	12
Assessment of eligibility	X								
Structured interview (MINI)	X								
Consent form	X								
Theta-burst stimulation (active/sham)			D	D	D	D	W	W	W
Clinical interviews	X		X	X		X	X	X	X
Adverse effects			X	X		X	X	X	X
Blood collection for serum biomarkers		X					X		
Neuropsychological evaluation		X					X		X
Cerebrospinal fluid collection		X							

“D” and “W” represent interventions performed daily and weekly, respectively.

Ethical aspects and safety

The rTMS is very safe when used properly and has few adverse effects, and as mentioned above, the most common is headache. Applications will always be made in a hospital setting with a physician present. We will evaluate patients 23 times over 12 weeks - so that we can quickly identify any worsening of the clinical picture and perform early intervention.

The study is approved by the Research Ethics Committee (CAAE: 80215117.5.0000.0068). All enrolled subjects will consent to participate through an Informed Consent Form. All the procedures described present minimal risk. If a volunteer presents a risk of major suicide, the same will be excluded from the study, adopting the standard procedure for the management of this type of patient. Participants may have access to their data and may leave the study at any time, without prejudice to any treatment they may perform within the institution. The data will be collected, analyzed and published in order to preserve the anonymity of the individual. In addition, the study will be conducted in accordance with all requirements of the Research Ethics Committee and also based on the recommendations established in the Declaration of Helsinki (1964), as amended in Tokyo (1975), Venice (1983) and Hong Kong (1989). As a benefit, participants will be able to participate in a clinical trial to treat their clinical condition. This

will be possible even if they receive sham stimulation, as they may receive active stimulation at the end of the study if they still have severe depressive symptoms.

Discussion

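### The safety section's 23 evaluations are the 23 stimulation sessions; only 6 post-baseline interviews and adverse-effect checks are scheduled, and nothing is specified for the remaining sessions

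*Combined protocol and SAP*

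**What the plan says.** The safety assurance is under Ethical aspects and safety: "We will evaluate patients 23 times over 12 weeks - so that we can quickly identify any worsening of the clinical picture". The sentence just before it says that stimulation is always given in hospital with a physician there.

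The number 23 appears elsewhere only as a count of sessions. Study Flow Chart has "TBS will be applied 23 times: 20 consecutive sessions (week 0 through week 4), 6th week, 8th week and 12th week". Interventions describes 20 daily sessions and then "A day of stimulation with the same technique will be done in the 6th week, 8th week and 12th week". The Discussion also refers to 23 sessions.

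The assessment schedule is smaller. In Table 1, the row "Clinical interviews" is marked at triage and at weeks 1, 2, 4, 6, 8 and 12. The row "Adverse effects" is marked at those same six weeks. Both rows are blank in week 3, while the stimulation row shows daily treatment that week. Clinical variables agrees on the times: "Outcomes will be measured on 7 occasions: baseline after 1, 2, 4, 6, 8 and 12 weeks of study entry". On safety measures it adds "The presence of adverse effects and the Young mania (YMRS) questionnaire will also be evaluated to detect manic and / or hypomanic cycling", without a separate timetable.

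Under Blinding, the person who applies the stimulation "will not be involved with the evaluations or with the evaluators, this person will be also blinded".

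**The concern.** The sentence on 23 evaluations is offered as a reason why participants are protected: frequent evaluation, hence early recognition of deterioration, hence early action. The trial enrols patients over 60 with HDRS above 17 who have been washed out of antidepressants, and one arm receives sham. A reader of the safety section will take 23 to be a number of planned assessments. The schedule that staff will follow contains 6 after baseline.

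There is also a data question. The abstract names the incidence of adverse events as a measure of tolerability and safety. If events are recorded only at the six marked visits, ascertainment depends on recall since the previous visit. Short-lived events such as headache, which the protocol names as the most common effect, are the ones most easily lost. If some staff note events at every session and others only at visits, recording will also be uneven between patients. The protocol does not say which is intended.

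**Working it through.** This is a count from the protocol's own schedule; no sample-size or power formula is involved.

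**1. Reproduce the stated figure.** Inputs from Interventions and Study Flow Chart: 20 daily sessions, plus single sessions in weeks 6, 8 and 12.

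20 + 3 = 23. The figure reproduces exactly as the number of stimulation sessions.

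One variant was considered. Design and population mentions return visits at weeks 4, 6, 8 and 12. If week 4 were an additional session, the total would be 20 + 4 = 24. Interventions, Study Flow Chart and the Discussion all support 23.

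**2. Try it as a count of scheduled assessments.** Table 1 marks after baseline:

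- Clinical interviews: weeks 1, 2, 4, 6, 8, 12 = 6
- Adverse effects: weeks 1, 2, 4, 6, 8, 12 = 6

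Adding the occasion before treatment gives 7, the number stated under Clinical variables. Neither 6 nor 7 matches 23. The difference is 23 − 6 = 17, and 17/23 = 74%.

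**3. Locate the difference.**

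| Period | Sessions | Scheduled checks | Difference |
|---|---|---|---|
| Weeks 0 to 4 | 20 | 3 (weeks 1, 2, 4) | 17 |
| After week 4 | 3 | 3 (weeks 6, 8, 12) | 0 |
| Total | 23 | 6 | 17 |

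All of the shortfall is in the daily course.

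**4. Intervals between scheduled checks.** From the start of treatment: 1, 1, 2, 2, 2 and 4 weeks. The 2-week interval from week 2 to week 4 is the one that spans daily stimulation with no check in week 3. The 4-week interval from week 8 to week 12 contains no session between its end visits, so it is not part of the mismatch.

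**5. An assumption.** Reading the 17 as sessions without a check assumes that each scheduled check falls on a session day. Design and population pairs session and evaluation at weeks 6, 8 and 12. For weeks 1, 2 and 4 the protocol does not say. If those three checks were all on separate days, 17 + 3 = 20 sessions would have none. The range is therefore 17 to 20 of 23. The difference between the two stated counts is 17 either way.

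**6. Is the week-3 gap a table-reading artefact?** It is blank in both rows, and week 3 is also missing from the list of times under Clinical variables. The sources agree, so the gap appears to be in the plan.

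**The case against.** The best defence is that Table 1 lists formal assessments while the safety section describes contact. Patients come to hospital 23 times, a physician is there each time, and deterioration could be seen at any of those contacts. On this reading 23 is a loose but honest description of clinical exposure. Much of this stands, and it rules out three stronger readings that a reader might infer.

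- *Early detection will not happen.* The documents do not show this. A schedule of formal assessments does not exclude clinical observation at sessions. What can be said is that the content of those contacts is unspecified.
- *A problem seen at a session has no route to anyone who can act.* The applicator is separated from evaluations and evaluators for blinding. Nothing bars that person from telling the physician who is present.
- *The 23 evaluations are the only safeguard.* They are not. Severe suicidal ideation is an exclusion criterion, the setting is a hospital with a physician, and there is a rule for participants who become a major suicide risk.

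It is also fair to object that under-counting of adverse events is possible but not demonstrated. The protocol does not say how events are elicited or over what recall period, and the first two intervals are only one week. Finally, nothing here bears on the primary comparison.

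The defence does not remove the inconsistency. Presence makes observation possible but does not define an evaluation, and no section assigns anyone to ask about or record anything at a session without a scheduled visit. If sessions are meant to count as evaluations, Table 1 is incomplete; if they are not, the safety sentence gives the wrong number.

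**Conclusion.** The point holds as an inconsistency between a safety assurance and the schedule, with an open question about how adverse events are recorded. The protocol states 23 evaluations and schedules 6 after baseline. The difference of 17 arises wholly in weeks 0 to 4, and week 3 has daily stimulation with no interview or adverse-effect check marked. Because a physician attends every session, the finding is that assessment and recording at the other sessions are not specified, not that surveillance is absent. Adverse-event incidence may be under-recorded; the documents give no basis for estimating by how much.

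The conclusion rests on reading Table 1 as the complete assessment schedule, which Clinical variables supports, and on a total of 23 sessions rather than 24. Severity is minor to moderate. Sample size, alpha and power are unaffected.

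**What to change.** Reconcile Ethical aspects and safety with Table 1 and Clinical variables. Either of two edits would do it:

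1. Mark adverse-effect recording, with date of onset, in Table 1 at every session day, including week 3, and say so under Clinical variables. The 23 evaluations would then exist as stated, and incidence would rest on a uniform record.
2. Keep the present schedule and restate the safety sentence as 6 scheduled post-baseline evaluations plus 23 session contacts with a physician present.

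The first improves adverse-event ascertainment during the daily course, at the cost of a little extra data entry at contacts that already take place. It would not shorten the interval from week 8 to week 12, which has no session inside it. The second is a change of wording only: it corrects the assurance but leaves ascertainment as it is. What any assessment of worsening or suicidality should contain, and how it is escalated, is for the sponsor to decide.

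### Randomised patients removed for major suicide risk have no later HDRS ratings planned; the resulting error has no fixed direction and is probably small, and one changed sentence would keep the ratings

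*Combined protocol and SAP*

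**What the plan says.** The combined protocol and SAP states under Ethical aspects and safety: "If a volunteer presents a risk of major suicide, the same will be excluded from the study". The patient then receives the usual management for such cases. Shortly before, the same section says patients are evaluated 23 times over 12 weeks so that worsening is found quickly. Entry is handled separately: Inclusion and exclusion criteria lists "presence of severe suicidal ideation" among the exclusions.

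Clinical variables sets the primary time point: "The primary evaluation will be done at the end of 6 weeks from the start of the first day of TBS". It also sets the rating schedule: "Outcomes will be measured on 7 occasions: baseline after 1, 2, 4, 6, 8 and 12 weeks of study entry". Neither that section nor Table 1 says whether ratings continue after removal.

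Statistical analysis promises: "All analyzes will be made on the intention to treat principle (ie the data of all participants will be included in the analysis". It adds that "lost data will be allocated according to the last observation carried forward principle and/or mixed data", and for the main outcome says "we will use a repeated measures analysis, having HDRS scores as Dependent variable". That section names week 8 where Clinical variables names week 6. Week 6 is used here; the argument is the same at week 8.

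**The concern.** Stopping stimulation and starting standard care is right for a patient at serious risk of suicide. The difficulty is that the rule, as written, appears to end measurement as well as treatment. The loss is imposed by the investigators, is triggered by worsening of the disease under study, and is avoidable.

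Neither method named for lost data clearly recovers these scores:

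- **LOCF** carries the last rated score. Patients are seen 23 times but rated at six visits after baseline, so a crisis found between ratings may never be scored. If it is scored, LOCF freezes the patient at the crisis level even if rescue care later helps.
- **A mixed model**, if that is what mixed data means, uses the patient's own earlier scores. It assumes that the patient then follows the course of similar patients who stayed in the same arm.

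At stake is the primary HDRS comparison, for removals before the primary time point. Without later ratings, the trial could not tell the direction of any error.

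**Working it through.** **1. Inputs from the documents.** The plan gives no figure on this point. Its only allowance for loss is a general one of about 25%: 86 x 1.25 = 107.5, rounded up to 108. Assuming 1:1 allocation, 108 / 2 = 54 per arm. Removing 5% is 2.7 patients per arm; removing 10% is 5.4.

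**2. Formula.** Let *gap* be the true week-6 HDRS minus the filled-in HDRS for a removed patient. Then

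error in TBS benefit = (share removed on TBS x gap on TBS) - (share removed on sham x gap on sham),

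where a positive value means benefit overstated. The true score is the one full follow-up would record, rescue care included. That is the intention-to-treat (treatment-policy) target.

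**3. Direction by hand, same gap in both arms (assumed values).**

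- Gap +5 (carried score precedes the crisis, patient stays worse). With 10% TBS / 5% sham: 0.10 x 5 - 0.05 x 5 = +0.25. With 5% / 10%: -0.25. With 5% / 5%: 0.
- Gap -8 (LOCF carries a crisis score of baseline + 3, rescue care brings the patient to baseline - 5). With 10% / 5%: 0.10 x (-8) - 0.05 x (-8) = -0.40. With 5% / 10%: +0.40.

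Each pattern of removal can therefore produce either sign.

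**4. Simulation.** All of the following are assumptions:

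- 54 per arm; true week-6 effect 3 or 4 points; sham mean 22 falling to 17; SD 4 at baseline rising to 7 at week 6; correlation 0.75 between adjacent visits.
- Removal after week 2, likelier with a higher week-2 score.
- Week-6 HDRS after removal equal to baseline, baseline + 3 or baseline - 5.
- Crisis score (baseline + 3) recorded at week 2, or not recorded.
- Four removal patterns.

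That makes 2 x 3 x 2 x 4 = 48 settings, with 2000 runs each. The mixed model is represented by sequential regression on arm and the patient's earlier scores. The Monte Carlo standard error of each error is at most 0.013.

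| Removed, TBS / sham | LOCF | Mixed model |
|---|---|---|
| 5% / 5% | 0.00 to +0.11 | +0.10 to +0.21 |
| 10% / 10% | 0.00 to +0.21 | +0.18 to +0.41 |
| 10% / 5% | -0.41 to +0.32 | +0.05 to +0.72 |
| 5% / 10% | -0.05 to +0.39 | -0.19 to +0.27 |

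The LOCF extremes of -0.41 and +0.39 agree with the hand values of -0.40 and +0.40 in step 3. Repeat runs moved the ends of the overall ranges by no more than 0.04 points.

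**5. Two settings in full** (baseline + 3 after removal, crisis not recorded).

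- Effect 4, 10% / 5%: full follow-up 3.23, LOCF 3.54 (+0.31), mixed model 3.94 (+0.71). As a rough check that ignores selection of worse patients, the TBS mean is 0.90 x 13 + 0.10 x 25 = 14.2 and the sham mean is 0.95 x 17 + 0.05 x 25 = 17.4, a difference of 3.2.
- Effect 3, 5% / 10%: full follow-up 3.13, LOCF 3.08 (-0.05), mixed model 2.94 (-0.19).

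The mixed model lands close to the assumed stimulation effect (3.94 against 4; 2.94 against 3). It misses the difference that includes what happens after removal.

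**6. Scale.** With SD 7, the standard error of the week-6 difference is 7 x sqrt(2/54) = 1.35. The largest error, 0.72, is 0.72 / 1.35 = 0.53 of a standard error.

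**The case against.** **The rule may only restate an entry criterion.** The sentence sits near the consent text and uses the language of exclusion. But entry is already covered elsewhere, and this sentence follows text on detecting deterioration during the study and is paired with clinical management. The on-study reading is the stronger one, though it remains an inference. A reader might go further and infer that later ratings are forbidden. The documents do not say so; they are silent, and the intention-to-treat sentence points the other way.

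**A mixed model is not simply biased.** This stands. The plan states no estimand, and the Discussion describes TBS as the sole antidepressant treatment after washout, which suits an on-treatment question. For that question the mixed model does well (step 5). The intention-to-treat wording supports measuring against the treatment-policy target, so the mixed-model figures are distances from that target only.

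**A reader might infer a direction:** more removals on TBS overstate benefit, more on sham understate it. The documents give no basis for this, and the table contradicts it as a rule. The largest understatement (-0.41) comes with more removals on TBS, and more removals on sham gives its larger errors as overstatement.

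**The effect is small and one part of a wider issue.** This also stands. Severe ideation is screened out at entry, the removal rates are assumed, and only removal after week 2 was simulated. Suicide-risk removals are probably a minority of the 25% loss allowed for. What sets them apart is that the plan itself imposes the loss because of a bad outcome.

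**Conclusion.** The point holds as a cheap improvement. On its most natural reading, the plan removes randomised patients because of a bad outcome and plans no HDRS ratings afterwards, which leaves its intention-to-treat promise to rest on LOCF or a mixed model. Against the treatment-policy week-6 difference, the error depends on the removal rates, on whether the crisis was scored and on the later course. Its sign is undetermined under either unequal pattern of removal. Equal removal does not guarantee zero either: the simulated mixed model still differed by +0.10 to +0.41.

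The size is about -0.4 to +0.7 HDRS points if 5% to 10% per arm are removed, and probably less in practice. The removal rates, effect, SD, correlation, timing and later course are all assumed. Nothing supports saying that the rule favours TBS or that it would alone decide the trial.

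**What to change.** 1. In Ethical aspects and safety, replace removal from the study with: *study stimulation stops, standard management starts, and the patient, if willing and if clinically safe, is still rated at the scheduled visits*.
2. Include these ratings in the intention-to-treat HDRS analysis.
3. Report the number and week of such discontinuations by arm.

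Optionally, add a sensitivity analysis giving an unfavourable week-6 score to patients who decline further ratings. The worse of the baseline and the last observed score is one reasonable choice among several.

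The cost is one changed sentence, a few ratings at visits already scheduled, and a line in the patient-flow report. The sample size does not change. The downsides are a few ratings of patients in crisis, some of whom will decline, and scores that reflect rescue treatment as well as the assigned arm. The latter is consistent with the intention-to-treat principle the plan has chosen.
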